5. SELECTION AND WITHDRAWAL OF SUBJECTS

5.1. Subject Inclusion Criteria

Subjects meeting all the following inclusion criteria at Screening/Day -1 will be eligible for participation in the study.

- 1) Female or male subjects, ≥ 18 years of age, able to understand and give written informed consent
- 2) Receiving ongoing treatment with sacituzumab govitecan in a Gilead (previously Immunomedics)-sponsored parent study
- 3) Continuing to receive clinical benefit from sacituzumab govitecan therapy
- 4) Creatinine clearance ≥ 30 mL/min as assessed by the Cockcroft-Gault equation.
- 5) Male subjects and female subjects of childbearing potential who engage in heterosexual intercourse must agree to use protocol-specified method(s) of contraception as described in [Appendix 4](#).

5.2. Subject Exclusion Criteria

Subjects meeting any of the following exclusion criteria at Screening/Day -1 of treatment will not be enrolled in the study.

- 1) Women who are pregnant or lactating ([Appendix 4](#))
- 2) Initiated therapy with another cancer therapeutic agent (investigational or standard of care) since receiving the last dose of the study drug on the parent study in which they participated
- 3) Experienced a toxicity from sacituzumab govitecan that resulted in permanent discontinuation of therapy
- 4) Have an active serious infection requiring IV antibiotics (Contact medical monitor for clarification)
- 5) Have other concurrent medical or psychiatric conditions that, in the Investigator's opinion, may be likely to confound study interpretation or prevent completion of study procedures and follow-up examinations

5.3. Criteria for Treatment Discontinuation

Subjects will discontinue the treatment under any of the following conditions:

- 1) Withdrawal of consent from further treatment with study drug
- 2) Lost to follow-up. Subjects will be considered lost to follow up when there is no response to two attempts one month apart by phone and a registered letter. After these 3 failed attempts, lost to follow-up will be documented
- 3) An adverse event (AE) that, in the opinion of the Investigator or the sponsor, contraindicates further dosing
- 4) Initiation of alternative anti-tumor therapy, including any investigational agent
- 5) Pregnancy
- 6) Disease progression with no evidence of clinical benefit
- 7) Loss of clinical benefit
- 8) Subject non-compliance
- 9) Sponsor terminates the study

5.4. Criteria for Study Discontinuation

Subjects will discontinue the study under any of the following conditions:

- 1) Death
- 2) Withdrawal of consent from study
- 3) Lost to follow-up. Subjects will be considered lost to follow up when there is no response to two attempts one month apart by phone and a registered letter. After these 3 failed attempts, lost to follow-up will be documented.
- 4) End of treatment, with documentation of resolution or stabilization of AEs (if applicable)
- 5) Sponsor terminates the study

6. TREATMENT OF SUBJECTS

6.1. Description of Study Drug

Sacituzumab govitecan is a humanized mAb with a hydrolysable linker through which SN-38 is conjugated to the humanized mAb hRS7 IgG1κ to enhance the delivery of SN-38 to Trop-2-expressing tumors, while reducing systemic toxicity. SN-38 is the active metabolite of irinotecan.

6.2. Investigational Medicinal Product, Dosage and Mode of Administration

Sacituzumab govitecan will be administered at the dose that the subject was receiving in the parent study at the time of consenting to participate in this rollover study. No dose escalation beyond the dose the subject was receiving in the parent study at the time of consenting to participate in this rollover study is permitted. No subject will receive more than 10 mg/kg dose of sacituzumab govitecan. Sacituzumab govitecan will be administered as an intravenous (IV) infusion on Days 1 and 8 of a 21-day cycle.

6.3. Treatment of Sacituzumab Govitecan-Associated Toxicities

Instructions for the infusion of sacituzumab govitecan are provided in Section 7.5. The following sections provide guidance for sacituzumab govitecan administration and management of treatment-related toxicities, including modification of dosing and treatment discontinuation. Toxicities should be managed in accordance with standard institutional practices and accepted treatment guidelines.

6.3.1. Preventative Medications

Infusion-Related Reactions: Premedication for prevention of infusion-related reactions (IRRs) with antipyretics and H1 and H2 blockers should be administered before each sacituzumab govitecan infusion. Corticosteroids (hydrocortisone 50 mg or equivalent orally [PO] or IV) may be administered prior to subsequent infusions. Additional details of recommended treatment of IRRs are described in Section 6.3.2.1.

Nausea, Vomiting: Sacituzumab govitecan is considered to be moderately emetogenic. Premedication with a 2-drug antiemetic regimen is recommended. If nausea and vomiting are persistent, a 3-drug regimen may be used, including a 5-HT3 inhibitor (ondansetron or palonosetron, or other agents according to local practices), an NK1-receptor antagonist (fosaprepitant or aprepitant), and dexamethasone (10 mg PO or IV). Anticipatory nausea can be treated with olanzapine. The recommended treatment of delayed nausea and vomiting is described in Section 6.3.2.2.

6.3.2. Management of Sacituzumab Govitecan Toxicities

NCI CTCAE v5.0 is used to grade the severity of all AEs. The guidelines for management of toxicities associated with sacituzumab govitecan are based on the assessment of severity according to these criteria. Toxicities should be managed in accordance with standard medical practice and treatment guidelines. All clinically appropriate imaging or laboratory testing should be utilized to fully assess a toxicity to determine the appropriate treatment. Appropriate follow-up-studies should be utilized to follow all toxicities to resolution. Subjects with known UGT1A1 *28 polymorphisms may have a higher risk of developing treatment-related toxicities. Additional monitoring may be required in those subjects. Subjects suspected of having underlying UGT1A1 *28 polymorphisms due to increased episodes of diarrhea or neutropenia, may have their polymorphism assessed per Investigator's discretion. Instructions for sacituzumab govitecan dose reduction for treatment-related toxicities are provided in Section [6.3.2.5](#).

6.3.2.1. Infusion-Related Reactions

Infusion-related reactions are defined as symptoms that occur during and within the first 6 hours after the infusion of sacituzumab govitecan and can occur at any cycle. Symptoms can include: fever, chills, rigors, arthralgias, myalgias, urticaria, pruritus, rash, diaphoresis, hypotension, dizziness, syncope, hypertension, dyspnea, cough, and wheezing, as well as severe hypersensitivity reactions including anaphylactic reactions. Infusion-related reactions should be treated in accordance with best clinical practices and standard institutional guidelines. Because of the potential for life-threatening IRRs, sacituzumab govitecan should only be administered in a setting in which appropriately trained medical staff, emergency equipment, and medications are available in the event that resuscitation is required. NCI CTCAE v5.0 is used to grade the severity of all infusion-related AEs. Premedication for the prevention of IRRs is described in Section [6.3.1](#).

Grade 4 Events

Grade 4 reactions include potentially life-threatening reactions, requiring urgent intervention. If Grade 4 IRRs occur, sacituzumab govitecan should be permanently discontinued ([Table 2](#)).

Grade 2 and Grade 3 Events

Grade 2 IRRs are defined as those that require infusion interruption and respond to symptomatic treatment; prophylactic medications are indicated for ≤ 24 hours. For Grade 2 IRRs, the infusion should be interrupted until symptoms resolve. After symptoms resolve, the infusion should be resumed at a slower infusion rate determined appropriate by the managing physician. Recommended infusion rates are provided in the Pharmacy Manual. Grade 3 IRRs are defined as those that are prolonged and do not improve with symptomatic treatment and/or brief interruption of treatment, reactions that recur following treatment, and reactions that require hospitalization. For recurrent Grade 2 or Grade 3 IRRs despite optimal management, sacituzumab govitecan should be permanently discontinued ([Table 2](#)).

6.3.2.2. Gastrointestinal Toxicities

Nausea, vomiting, and diarrhea are frequent sacituzumab govitecan-associated toxicities. Appropriate treatment, including, as needed, fluid and electrolyte replacement, is required to minimize the risk of serious consequences such as dehydration. Instructions for sacituzumab govitecan dose reduction for treatment-related gastrointestinal toxicities are provided in Section [6.3.2.5](#).

Nausea and Vomiting

Instructions for the use of premedications for prophylactic treatment of nausea and vomiting and anticipatory nausea are provided in Section [6.3.1](#). Withhold sacituzumab govitecan for Grade 3 nausea or Grade 3 or 4 vomiting at the time of scheduled treatment administration and resume with additional supportive measures when resolved to Grade ≤ 1 . Manage this toxicity per standard institutional guidelines.

Diarrhea

Dietary modification should be recommended for the management of diarrhea, including adequate fluid intake to maintain hydration. Loperamide can be administered at the onset of treatment-related Grade 1 or Grade 2 diarrhea, at an initial dose of 4 mg, followed by 2 mg with every episode of diarrhea to a maximum dose of 16 mg/day. If diarrhea is not resolved after 24 hours, consider adding diphenoxylate/atropine and/or opium tincture, as clinically indicated.

Add octreotide 100-150 μ g subcutaneous (SC) three times per day (tid) if diarrhea persists. Withhold sacituzumab govitecan for Grade 3 or 4 diarrhea at the time of scheduled treatment administration and resume when resolved to Grade ≤ 1 . For Grade 3 or Grade 4 diarrhea, consider hospitalization, and treat with IV fluids, and octreotide. Antibiotics can be administered as clinically indicated.

Subjects who exhibit an excessive cholinergic response to treatment with sacituzumab govitecan (eg, abdominal cramping, diarrhea, salivation, etc.) can receive appropriate premedication (eg, atropine) for subsequent treatments.

6.3.2.3. Neutropenia

Complete blood counts (CBC) must be obtained prior to each sacituzumab govitecan infusion. Sacituzumab govitecan should be administered only if absolute neutrophil counts (ANC) meet the following criteria:

- Day 1: ANC $\geq 1500/\text{mm}^3$
- Day 8: ANC $\geq 1000/\text{mm}^3$

Sacituzumab govitecan should not be administered in cases of neutropenic fever.

The routine prophylactic use of growth factors is not required; however, prophylactic administration may be considered and should comply with American Society of Clinical Oncology (ASCO) guidelines for use of growth factors. They may be used in subjects who have experienced febrile neutropenia or Grade 3 or Grade 4 neutropenia following previous infusions. Growth factors may also be administered in the setting of neutropenia in subjects at high risk of poor clinical outcomes, including those with prolonged neutropenia, ANC <1000/mm³, febrile neutropenia, and serious infections.

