6.3.2.5. Sacituzumab Govitecan Dose Modification Guidelines

Dose Delays

Sacituzumab govitecan is to be administered in 21-day cycles on Day 1 and Day 8; the next cycle should start a minimum 14 days after the Day 8 dose (ie, the Day 8 infusion will be counted as the first day of that 14-day period). Dosing 1 day prior to and 7 days after the scheduled infusion are permitted. The scheduled Day 1 and Day 8 infusions may be delayed for up to one week for treatment-related toxicities.

Instructions for dose delays and dose reductions for specific toxicities are summarized below. For toxicities not specifically addressed in the toxicity management table ([Table 2](#)), dosing may be delayed for > Grade 2 toxicities for a maximum of one week. If the toxicity has improved to ≤ Grade 2, the dose should be administered at that time. For a toxicity that delays Day 8 dosing, if the toxicity has not resolved to ≤ Grade 2 within one week, dosing should resume with the next scheduled cycle, ie, the next dose will be Day 1 of the following cycle. Regardless of whether the Day 8 dose is delayed for toxicity, there should be a minimum of 14 days between the Day 8 infusion and the Day 1 infusion of the next cycle (day of delay is counted as day 1 of this 14-day period).

Dose Reductions and Discontinuation

The major toxicities of sacituzumab govitecan are expected to be gastrointestinal symptoms and hematologic suppression. All subjects will be closely monitored over the course of their treatment and aggressively medically managed, including dose reduction and interruption, in order to prevent the need for treatment discontinuation and serious complications of these toxicities. All efforts to avoid dose reduction should be taken to address toxicity prior to institution of dose reduction. Sacituzumab govitecan dose reductions and interruptions will be managed based on toxicity severity, as assessed by NCI CTCAE v5.0. Leukopenia or lymphopenia in the absence of neutropenia will not require dose delay or dose modification. The dose of sacituzumab govitecan **must not** be re-escalated following a dose reduction. [Table 2](#) summarizes recommendations for sacituzumab govitecan dose reductions and discontinuations for treatment-related toxicities.

Table 2.

Recommended Dose Modification Schedule for Sacituzumab Govitecan

Adverse Reaction	Occurrence	Dose Modification or Action
Severe neutropenia		

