Grade 4 neutropenia \geq 7 days, OR	First	25% dose reduction and administer G-CSF
Grade 3-4 febrile neutropenia, OR	Second	50% dose reduction
At time of scheduled treatment, Grade 3 or 4 neutropenia that delays dosing by 2 or 3 weeks for recovery to \leq Grade 1	Third	Discontinue treatment
At time of scheduled treatment, Grade 3 or 4 neutropenia that delays dosing beyond 3 weeks for recovery to \leq Grade 1	First	Discontinue treatment
Severe nonneutropenic toxicity		
Grade 4 nonhematologic toxicity of any duration, OR	First	25% dose reduction
Any Grade 3 or 4 nausea, vomiting, or diarrhea due to treatment that is not controlled with antiemetics and antidiarrheal agents OR	Second	50% dose reduction
Other Grade 3 or 4 nonhematologic toxicity persisting $>$ 48 hours despite optimal medical management, OR	Third	Discontinue treatment
At time of scheduled treatment, Grade 3 or 4 nonneutropenic hematologic or nonhematologic toxicity that delays dose by 2 or 3 weeks for recovery to \leq Grade 1		
In the event of Grade 3 or 4 nonneutropenic hematologic or nonhematologic toxicity that does not recover to \leq Grade 1 within 3 weeks	First	Discontinue treatment
Infusion-Related Toxicities		
Grade 2 or Grade 3 infusion-related reaction despite optimal management	Recurrent	Discontinue treatment
Grade 4 infusion-related reaction	First	Discontinue treatment

G-CSF = granulocyte colony-stimulating factor; NCI-CTCAE = National Cancer Institute-Common Terminology Criteria for Adverse Events

Refer to Section 10.2.2.6 for the NCI-CTCAE severity grading details.

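### Protocol Sections 6.3.2.3 and 6.3.2.5 and Table 2 do not say what ends a Day 8 neutropenia hold or how the delay is counted, so the same counts can lead to the current dose, a reduction or discontinuation

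*Protocol*

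**What the plan says.** Three places in the protocol bear on a neutropenia hold.

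- **Section 6.3.2.3 (Neutropenia)** sets minimum counts for giving an infusion: "Sacituzumab govitecan should be administered only if absolute neutrophil counts (ANC) meet the following criteria", namely 1500/mm³ or more on Day 1 and 1000/mm³ or more on Day 8.
- **Table 2 (Section 6.3.2.5)** sets the dose consequence. One row reads "At time of scheduled treatment, Grade 3 or 4 neutropenia that delays dosing by 2 or 3 weeks for recovery to" Grade 1 or less. The action at first occurrence is "25% dose reduction and administer G-CSF", at the second a 50% reduction, and at the third discontinuation. A further row, "Grade 3 or 4 neutropenia that delays dosing beyond 3 weeks for recovery to" Grade 1 or less, leads to discontinuation at first occurrence. Neither row separates Day 1 from Day 8.
- **Dose Delays (Section 6.3.2.5)** allows Day 1 and Day 8 infusions to be put back by up to one week for treatment-related toxicity.

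Footnote c of the Schedule of Assessments and Section 10.1.2.1 send sites to Section 6.3.2.3 for the count needed before dosing. Section 6.3.2 sends them to Section 6.3.2.5 for dose reduction. No text gives one precedence over another. Grading is by CTCAE v5.0, whose neutrophil cut-offs are not printed.

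**The concern.** After a Day 8 infusion is held for Grade 3 or 4 neutropenia, a site needs to know two things: which count ends the hold, and from which date to which date the Table 2 delay is measured. The protocol answers neither. It also sets a one-week limit on delays beside rows that act only on delays of two weeks or more.

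Section 1.3.4 lists neutropenia among the most frequent reasons for treatment modification and among the frequent reasons for permanent discontinuation. Section 6.3.2.5 forbids re-escalation after a reduction, so a reduction that turns on a site's reading cannot be undone. Enrolled subjects are, by inclusion criterion 3, still benefiting.

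Differences between sites would also enter the exposure summaries (SAP Section 6.1: reductions, delays, relative dose intensity), the tables of adverse events leading to reduction, interruption or discontinuation (SAP Section 6.2), and the same tables for the neutropenia group of special interest (SAP Section 6.3).

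**Working it through.** The plan gives no figure to reproduce. The check sets the rules side by side and runs example counts through them.

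**Inputs from the protocol.** Minimum counts 1500 (Day 1) and 1000 (Day 8); Table 2 bands of 2 or 3 weeks and beyond 3 weeks; a one-week delay limit; a 21-day cycle with at least 14 days from the Day 8 infusion to the next Day 1.

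**Assumptions.** Grade 1 or less means a count of at least c, with c = 1500; Grade 3 starts below 1000. The examples are first occurrences, without fever, with no count in Grade 4.

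**Step 1: can one recovery target match both minimum counts?** A single c cannot equal both 1500 and 1000. The mismatch lies between each day's minimum and c:

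| c (/mm³) | Day 8 mismatch | Day 1 mismatch |
|---|---|---|
| 1000 | none | 1000–1499 |
| 1250 | 1000–1249 | 1250–1499 |
| 1500 | 1000–1499 | none |
| 1800 | 1000–1799 | 1500–1799 |
| 2000 | 1000–1999 | 1500–1999 |

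The value 1000 is a limiting case: with Grade 3 starting below 1000 it would leave no Grade 2.

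**Step 2: example counts, c = 1500.** Counts are weekly from the held Day 8 (week 0). Reading A ends the hold at the Day 8 minimum. Reading B ends it at Grade 1 or less. Reading C applies the one-week limit: if the Day 8 minimum is not met by week 1, Day 8 is omitted and the next infusion is Day 1.

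| Weekly counts | A | B | C |
|---|---|---|---|
| 800, 1200, 1600 | week 1: current dose | week 2: 25% reduction | week 1: current dose |
| 800, 1200, 1200, 1200, 1200, 1600 | week 1: current dose | week 5: discontinue | week 1: current dose |
| 800, 900, 1200, 1300, 1400, 1600 | week 2: 25% reduction | week 5: discontinue | no Table 2 row met |

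**Step 3: where the delay starts.** Two weeks after Day 8 is Day 8 + 14 = Day 22, which is the next Day 1. In the third series the count that day is 1200. This is below the Day 1 minimum, so dosing still waits, but it is not Grade 3 or 4, so the Table 2 row does not start there. The count first reaches 1500 at week 5: 5 weeks from the held Day 8, but 5 − 2 = 3 weeks from the next Day 1. Setting c = 1000 makes A and B agree on this series (25% reduction), but C still gives no Table 2 action. The counting question therefore remains even when the Day 8 thresholds coincide.

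**Step 4: the one-week limit.** One week is shorter than two. If the limit stops every hold of a single infusion, no such hold can reach the 2-or-3-week row. The row can be reached only if the limit does not bind for neutropenia, or if delay accumulates across an omitted Day 8 and the next Day 1. The protocol says neither.

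**The case against.** The best reply is that the texts do different jobs. Section 6.3.2.3 sets a minimum count for dosing; Table 2 sets the consequence of a long delay to dosing. A Day 8 infusion given one week late at a count of 1200 has not been delayed by 2 or 3 weeks, so no row applies. Withholding it longer would mean ignoring a Day 8 minimum already met and the one-week limit. By the next Day 1, under the assumed cut-off, the Day 1 minimum and Table 2 agree.

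Much of this stands. A reader might infer that two minimum counts against one recovery target are a contradiction in themselves. They are not: a dosing minimum and a recovery target can coexist. But the harmonising reading is nowhere stated. A minimum worded as a necessary condition does not exclude a further recovery requirement in Table 2. Nor does this reading settle the third series, where the Day 8 minimum is met only after the one-week limit has passed.

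A reader might also take the sentence "If the toxicity has improved to ≤ Grade 2, the dose should be administered at that time" as another neutropenia threshold. It belongs to the paragraph on toxicities that Table 2 does not address, so it should not be cited as one.

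On scale, Section 1.3.4 says neutropenia arose in the first cycle and resolved in about a week, and subjects enter already tolerating therapy, so long holds may be uncommon. Table 2 is headed as a recommendation. The primary endpoints in Section 11.3.1 (any adverse event, serious adverse event or laboratory abnormality) do not count dose modifications.

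**Conclusion.** The concern holds as a gap in the rules together with an unreconciled one-week limit. With Grade 1 ending at 1500/mm³ and Grade 3 starting below 1000/mm³, the dispute is confined to counts of 1000 to 1499/mm³ after a Day 8 hold. In that band the same counts can lead to continuing the current dose, or to reduction or discontinuation, depending on the text followed. Two of the three example series give two outcomes. The third gives three, but only because the one-week limit is added as a separate reading. A different Grade 1 cut-off moves the mismatch to Day 1 or extends it there.

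How many subjects would be affected cannot be estimated from the documents. The documents also do not support describing the favourable outcome as full dose: subjects may enter on a dose already reduced in the parent study. The point merits correction because a reduction or discontinuation cannot be reversed and the correction is cheap.

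**What to change.** Reconcile Section 6.3.2.3, the one-week limit in Section 6.3.2.5 and the neutropenia rows of Table 2 so that one rule states, separately for Day 1 and Day 8:

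- what ends a neutropenia delay;
- on which date the Table 2 delay starts and stops, including when Day 8 is omitted;
- how the one-week limit relates to the 2-or-3-week and beyond-3-week rows;
- which text governs if they differ.

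The clinical team decides the values.

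The SAP's approach needs no change: it should go on summarising reductions, delays and discontinuations as they actually occurred. Deriving them from a protocol rule would replace what happened with what should have happened.

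The cost is wording in the next amendment and a clarification letter to sites. No new data collection is needed.

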6.3.2.4. Overdose

Overdose is defined as administration of a dose that is 10% higher than the calculated dose. In the event of an overdose, closely monitor the subject per standard institutional guidelines. Any AE resulting from overdose should be reported as described in Section [10.2.2](#).

